# PARTNERS HUMAN RESEARCH COMMITTEE

## DETAILED PROTOCOL

### II. SPECIFIC AIMS

- 1) *To document changes in body composition (visceral adiposity) and insulin sensitivity (homeostatic model assessment) resulting from FES-RT in comparison to a time (wait-list) control and to arms-only row training (arms-only-RT)*

We hypothesize FES-RT will mitigate against increased visceral adiposity and reduced insulin sensitivity occurring with acute SCI and that FES-RT will be more effective than arms-only-RT.

- 2) *To quantify changes in key indices of cardiovascular health (serum lipids) and control (arterial baroreflex gain) with FES-RT in comparison to a time control and to arms-only-RT*

We hypothesize FES-RT will prevent the worsening lipid profile and compromised baroreflex function occurring with acute SCI and that FES-RT will be more effective than arms-only-RT.

- 3) *To characterize changes in myocardial structure (left ventricular wall thickness) and function (left ventricular diastolic velocity) with FES-RT in comparison to a time control and to arms-only-RT*

We hypothesize FES-RT will counter the ventricular wall thickening and declining ventricular function occurring with acute SCI and that FES-RT will be more effective than arms-only-RT.

- 4) *To compare the body composition, insulin sensitivity, cardiovascular health and control, and myocardial structure and function and the magnitude of adaptations to FES-RT across a range of injury duration from acute to chronic SCI.*

We hypothesize that cross-sectional declines in all variables will relate directly to injury duration and that therefore the magnitude of adaptations will be greater with longer injury duration.

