### III. SUBJECT SELECTION

We will enroll 60 individuals within twelve months post SCI to obtain data on 50 individuals. One-half of the subjects (N=25) will be randomized to immediately enroll in 6 months of FES-RT. One third (N=18) will be randomized to a wait-list to provide time control data from baseline to 6 months. A wait-list control group is routine in exercise studies because most volunteers are interested in participating in an exercise program. Hence, time controls are difficult to capture since many of those randomized to receive

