## PARTNERS HUMAN RESEARCH COMMITTEE

### DETAILED PROTOCOL

no exercise either drop from the study entirely, or end up pursuing some form of exercise on their own. Therefore, a vehicle for enrollment of a time control group that is acceptable to most volunteers is a wait-list. A six month time control will provide data on expected declines. One-third (N=17) of subjects will be randomized to six months of arms-only-RT. This will provide data on a comparator that represents a form of arms-only exercise that would be available to those with SCI. These subjects will undergo six months of FES-RT after completing arms-only-RT. This will enhance subject retention and provide data for secondary analysis.

To enhance subject recruitment we may enroll subjects into the study before they are 3-months post injury, most likely while they are still in-patients at Spaulding Rehabilitation Hospital. This will help subjects to schedule and plan for transportation for study assessments and training to begin when they reach 3-months post injury. No study assessments will be scheduled before 3-months from time of their SCI. Study participation will not interfere with scheduling of any normal inpatient therapy, nor will study participation take place during normal therapy. In-patients will need to be cleared to participate by their treating physician.

In addition we will enroll another 25 individuals with chronic SCI to serve as a comparator to the acute FES-RT group. Neither a wait-list nor arms-only-RT are required for this population. Time control data from baseline to 6 months are not needed since expected declines would be minimal over this time period after the acute phase of injury. In addition, the fourth aim is solely focused on responses to FES-RT and so a comparator that represents a form of arms-only exercise available to those with SCI is not necessary. Subjects in the chronic group will be at least 1 year post spinal cord injury with adult onset of SCI(SCI occurrence after 18 years of age).

All volunteers will continue with regular physical rehabilitation except for modalities that overlap study interventions (e.g., FES-cycling).

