### **Study Assessments**

Most Assessments will be performed at baseline and after 3 and 6 months for each study group. The DXA measurements and the AO-VO2max test (for the FES-RT group only) will only be performed at baseline and after 6 months. The Arms-only-RT and Wait-list groups will immediately enter baseline FES-RT protocol after completing all study procedures required in their initial group. Their six month lab visit and DXA scan data will also be used as their baseline FES-RT measures. Subjects may be asked to repeat any of the study assessments if there is difficulty obtaining results that meet our quality standards or there are equipment issues that arise.

Subjects that take longer than eight weeks to progress to performing their baseline FES-VO2max test will perform an extra assessment around the time of their baseline FES-VO2max test to account for changes that may occur over that time period. This extra study session will consist of: height, weight and circumference measures, blood samples, health questionnaires, pulmonary function tests, resting cardiovascular hemodynamics and neck suction-baroreflex testing. This extra testing session will take about 2-hours and can be done on a normal training day.

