## VI. BIOSTATISTICAL ANALYSIS

Power analysis: Based on longitudinal exercise capacity data from our lab, extensive sets of power analyses were performed. For the main analysis (acute subjects only), there will be 3 groups of subjects (FES-RT, wait-list and arms-only-RT) and measures at baseline, 3 months, 6 months, except for visceral adiposity (only at baseline and 6 months). The primary analysis (below) will include the three groups and will have as predictors two indicator (dummy) variables for two of the groups, and indicators for the 3 month and 6 month time points and interactions between the time points and the group indicator variables; this will be estimated as a linear mixed model. The only random effect will be for subject. In addition, for the fourth aim, the analysis will only include those entered into FES-RT at the outset, i.e., the FES-RT with acute SCI and all

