## PARTNERS HUMAN RESEARCH COMMITTEE

### DETAILED PROTOCOL

volunteers with chronic SCI. The main analysis will consist of comparisons across time with injury duration as a covariate.

Given logistical constraints, we began with the assumption that data on 50 acute SCI subjects (out of 60 recruited - a ~15% dropout rate) would be advantageous if that sample size allowed us to find differences that are substantively meaningful. This group would be allocated (randomly; see below) as 40% to FES-RT and 30% to each of wait-list and arms-only-RT. We also checked other total sample sizes and allocation rules (e.g., data from 20 in each group, data from 25 in FES and 15 in each of the other two groups). In addition, 25 individuals with chronic SCI would provide sufficient power to detect meaningful (e.g., >15%) differences between acute and chronic SCI at the same power outlined below.

These calculations were performed assuming an alpha of 0.05 and a correlation between baseline and 6 month measure of about 0.7; unless the correlation was very different from 0.7 (e.g., 0.25), there was little difference in the results. This shows that we will have sufficient power under this plan with a sample size of 50 acute SCI subjects and allocation of 20/15/15. Subjects will be randomized at the ratio of 1.33:1:1 to each of the three groups by a randomization plan constructed by the project statistician. The investigator will have no knowledge of group assignment until the time of subject enrollment. During the study, there can be no blinding of the subject or the investigator, however all measures will be obtained by an individual blind to subject group assignment.

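### Aim 4 states a cross-sectional injury-duration hypothesis, but its single analysis set leaves out the baselines of the wait-list and arms-only acute subjects

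*Combined protocol and SAP*

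**What the plan says.** Section II (Specific Aims) gives Aim 4 two linked hypotheses. The first is cross-sectional: "We hypothesize that cross-sectional declines in all variables will relate directly to injury duration". The second, drawn from the first, is that adaptation to FES-RT will be larger at longer injury duration.

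Section III (Subject Selection) describes the aim more narrowly. In explaining why the chronic cohort needs no arms-only comparator, it says "the fourth aim is solely focused on responses to FES-RT".

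Section VI (Biostatistical Analysis) defines the analysis set once for the whole aim: "for the fourth aim, the analysis will only include those entered into FES-RT at the outset", which it spells out as the acute FES-RT subjects together with the whole chronic cohort. It then describes the analysis in one sentence: "The main analysis will consist of comparisons across time with injury duration as a covariate". It gives no separate set or model for the cross-sectional hypothesis.

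Section V (Study Assessments) says "Most Assessments will be performed at baseline and after 3 and 6 months for each study group". The Study Procedure Time Line lists a lab visit and a DXA scan at baseline for the wait-list and arms-only groups as well as for FES-RT.

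On numbers, section III says "We will enroll 60 individuals within twelve months post SCI to obtain data on 50 individuals", split 25 FES-RT, 18 wait-list and 17 arms-only, with 25 chronic subjects in addition. Section VI gives a randomisation ratio of 1.33:1:1 and 20/15/15 subjects with data.

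**The concern.** Only the adaptation hypothesis needs subjects who go straight into FES-RT. The cross-sectional hypothesis needs a baseline measurement and an injury date, and every acute arm supplies both. As section VI stands, more than half of the acute baselines play no part in that hypothesis.

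The one analysis described does not clearly test it either. Section VI does not say whether the model has a duration-by-time term. Without one, a duration coefficient would average over visits during and after training and would not describe status at baseline.

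What is at stake is the precision of the first half of Aim 4, on which section II rests the second half. The excluded subjects are all within twelve months of injury, the period in which section I places the profound decline.

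**Working it through.** **1. Subjects outside the Aim 4 set**

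- Section III: 25 + 18 + 17 = 60, which reproduces the enrolled total. Outside the set: 18 + 17 = 35 of 60 (58%).
- Section VI ratio applied to 60: 24/18/18, so 36 of 60 (60%).
- Section VI subjects with data: 15 + 15 = 30 of 50 (60%).

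Sections III and VI disagree on allocation, but this barely moves the excluded share.

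**2. The plan's own power statement**

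Section VI says that 25 chronic subjects suffice to detect acute-chronic differences above 15%. It gives no SD and no numeric power, so the statement cannot be reproduced. The results below are therefore in SD units.

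**3. Acute-chronic contrast at baseline**

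SE = SD × √(1/n_acute + 1/n_chronic). Detectable difference at 80% power = (1.96 + 0.84) × SE, with two-sided alpha 0.05 assumed because the plan does not state sidedness. The chronic group is 25 throughout.

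| Acute n | SE (SD units) | Detectable difference (SD) |
|---|---|---|
| 25 (section III, FES-RT only) | √(1/25 + 1/25) = 0.283 | 0.79 |
| 60 (all enrolled) | √(1/60 + 1/25) = 0.238 | 0.67 |
| 20 (section VI, FES-RT only) | √(1/20 + 1/25) = 0.300 | 0.84 |
| 50 (all with data) | √(1/50 + 1/25) = 0.245 | 0.69 |

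SE reduction on enrolled numbers: 1 − 0.238/0.283 = 16%. On subjects with data: 1 − 0.245/0.300 = 18%. The figure for 60 is an upper bound on sample size, because it assumes that everyone enrolled reaches baseline.

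**4. Power at assumed true differences**

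| True difference (SD) | 25 v 25 | 60 v 25 | 20 v 25 | 50 v 25 |
|---|---|---|---|---|
| 0.5 | 42% | 56% | 39% | 53% |
| 0.6 | 56% | 71% | 52% | 69% |
| 0.7 | 70% | 84% | 65% | 82% |
| 0.8 | 81% | 92% | 76% | 90% |

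**5. Slope on injury duration**

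The SE of a slope is proportional to 1/√Σ(x − x̄)². The plan gives no duration distribution, so I assumed acute durations uniform on 0.25-1 year and chronic durations uniform from 1 year to 5, 10 or 20 years, on a linear or log scale. Over 4,000 simulated samples per setting, the ratio of SE with all acute arms to SE with FES-RT only ran from 0.81 to 0.89, a reduction of about 11-19%. The log scale gains more than the linear scale.

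For a slope within acute subjects alone, the ratio is √(25/60) = 0.65 or √(20/50) = 0.63, a reduction of 35-37%.

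**The case against.** The best defence is section III: if the aim concerns only responses to FES-RT, the restriction in section VI follows. That holds for the adaptation hypothesis, where the restriction is sound. It does not dispose of the cross-sectional hypothesis, which section II states outright. The two sections are at odds, and section VI follows the narrower one.

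Second, section VI calls its sentence the main analysis, which does not rule out a further baseline analysis in a wider set. That is fair. The accurate description is that no cross-sectional model is written out and the only set given for the aim is the restricted one. A reader might infer that the plan deliberately tests the cross-sectional hypothesis in FES-RT starters alone, but the text does not go that far.

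Third, a reader might infer that the restriction biases the result or that the baselines are thrown away. Neither follows. The FES-RT arm is a random subset of the acute subjects, and Aims 1 to 3 use the baselines of all three arms.

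Fourth, it is tempting to call the omitted baselines untrained and fully interchangeable with the rest. Section V offers FES-strength training before the first assessments to anyone enrolled before 3 months post injury. Section VI conceals assignment only until enrolment, so for these subjects baseline may follow both some training and knowledge of the arm. This can happen in any acute arm, so it is no reason to exclude two of them, but it calls for a sensitivity analysis.

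Finally, the gain is limited by the 25 chronic subjects: adding about 60% of the acute baselines cuts the SE by less than a fifth.

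**Conclusion.** The point holds as a matter of efficiency. Sections II and III disagree on the scope of Aim 4. The single analysis set in section VI leaves 58-60% of acute baselines out of a hypothesis they inform. Including them reduces the SE of the acute-chronic contrast by 16-18% and that of a slope across the whole sample by about 11-19%.

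The contrast figures assume equal variances and two-sided alpha 0.05; the slope range rests on the assumed durations. The number of subjects who will reach baseline is unknown, since early enrollees have only a partial screening visit at first. It will be lower for the echocardiographic variables in anyone whose baseline falls after 1/1/19, when section V stops those measurements.

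A reader might also infer that the restricted set is underpowered for the 15% target. The documents cannot show that, because they give no SD. No primary conclusion is affected, and the change is an optional precision gain for a non-primary, non-randomised comparison.

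**What to change.** In section VI, split the Aim 4 analysis:

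- **Cross-sectional hypothesis:** a baseline-only regression of each outcome on injury duration, in all acute subjects of all three arms who have a baseline plus all chronic subjects. Add a sensitivity analysis that adjusts for, or excludes, acute subjects who did FES-strength training before baseline.
- **Adaptation hypothesis:** keep the present set of acute FES-RT starters plus chronic subjects.

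In section III, reword the statement of Aim 4's focus so that it agrees with section II.

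The cost is a few sentences of text. No new subjects, visits or measurements are needed, provided that training before baseline is recorded for each early enrollee.

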## PARTNERS HUMAN RESEARCH COMMITTEE

### DETAILED PROTOCOL

volunteers with chronic SCI. The main analysis will consist of comparisons across time with injury duration as a covariate.

Given logistical constraints, we began with the assumption that data on 50 acute SCI subjects (out of 60 recruited - a ~15% dropout rate) would be advantageous if that sample size allowed us to find differences that are substantively meaningful. This group would be allocated (randomly; see below) as 40% to FES-RT and 30% to each of wait-list and arms-only-RT. We also checked other total sample sizes and allocation rules (e.g., data from 20 in each group, data from 25 in FES and 15 in each of the other two groups). In addition, 25 individuals with chronic SCI would provide sufficient power to detect meaningful (e.g., >15%) differences between acute and chronic SCI at the same power outlined below.

These calculations were performed assuming an alpha of 0.05 and a correlation between baseline and 6 month measure of about 0.7; unless the correlation was very different from 0.7 (e.g., 0.25), there was little difference in the results. This shows that we will have sufficient power under this plan with a sample size of 50 acute SCI subjects and allocation of 20/15/15. Subjects will be randomized at the ratio of 1.33:1:1 to each of the three groups by a randomization plan constructed by the project statistician. The investigator will have no knowledge of group assignment until the time of subject enrollment. During the study, there can be no blinding of the subject or the investigator, however all measures will be obtained by an individual blind to subject group assignment.

*Primary data analysis:* The primary analysis will test whether the FES-RT has 'better' values of the outcome variables at 6 months post-baseline. A general linear mixed model with a random effect for subjects will be used to conduct an intent-to-treat analysis. The main predictors will be indicator variables for group with the FES-RT group as the reference group and indicators for each of the other two groups, the time at which the outcomes were measured and treatment group by time interactions; menstrual status (with men coded the same as women who are not menstruating) will be included as a dummy variable; for the insulin resistance measure, body weight/fat changes will be included as a predictor. In a secondary analysis, we will include interactions terms between the group indicators and the 3 month indicator. In addition, similar models to the above will be estimated for secondary outcomes.

*Checking and Sensitivity Analyses:* It is important to ensure that data idiosyncrasies do not impact the results and that the results are generalizable. We will check for systematic differences between the model and the data using graphs, such as comparisons of predicted and observed values of the outcome variable, and other standard diagnostics. An extension of this idea is to simulate new sets of data based on our model and use the simulated data as a reference test group by comparing this to the observed data; we do this to look for situations in which the data appear different

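### Aim 4 names no duration-by-time term for its adaptation hypothesis, and if adaptation means effect net of expected decline, comparing change by injury duration is tilted toward that hypothesis

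*Combined protocol and SAP*

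**What the plan says.** Section II gives Aim 4 two hypotheses. The first concerns level: "cross-sectional declines in all variables will relate directly to injury duration". The second concerns response to training: "the magnitude of adaptations will be greater with longer injury duration".

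The analysis text is in Section VI, under the power analysis. It fixes the analysis set: "for the fourth aim, the analysis will only include those entered into FES-RT at the outset", meaning the acute FES-RT arm and all chronic volunteers. The model is then described in one sentence: "The main analysis will consist of comparisons across time with injury duration as a covariate". For the acute three-group model, by contrast, the same section lists "interactions between the time points and the group indicator variables".

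On untreated change, Section III says the acute wait-list is there to supply data on expected six-month declines. For the chronic group it says: "Time control data from baseline to 6 months are not needed since expected declines would be minimal over this time period". Aims 1-3 describe benefit in acute SCI as offsetting a worsening, for example "We hypothesize FES-RT will mitigate against increased visceral adiposity and reduced insulin sensitivity occurring with acute SCI". Aim 4 does not say whether adaptation means observed change or effect net of decline.

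**The concern.** There are two linked problems.

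- **The test is not named.** Greater adaptation with longer duration is a duration-by-time effect. If duration enters only as a main effect, every subject shares one time effect and the model cannot express different adaptation. A significant duration coefficient would speak to the level hypothesis and could be misreported as adaptation.
- **The likely alternative is not neutral.** If change is compared by duration, acute change contains the training effect plus the expected decline, while chronic change is close to the training effect alone. On a net-of-decline meaning, the gap favours longer duration, which is the direction the aim predicts. The data that measure the decline lie outside the Aim 4 set.

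At stake is what Aim 4 can conclude from the 25 chronic subjects enrolled for it. The randomised comparisons in Aims 1-3 are not touched.

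**Working it through.** **Inputs from the documents (Section VI).** 20 acute FES-RT subjects with data (20/15/15 allocation), 25 chronic, alpha 0.05, correlation r between baseline and 6 months of about 0.7. The plan names 0.25 as a value that would matter: "unless the correlation was very different from 0.7 (e.g., 0.25), there was little difference in the results". Section III gives eligible ages 18-40 and adult onset, so chronic duration runs from 1 to at most 40 − 18 = 22 years.

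**Assumed.** Two-sided testing; acute decline D of 0.1, 0.25, 0.50 or 0.75 SD; chronic decline 0; equal true training effects; acute duration uniform over 0.25-1 year; chronic duration uniform 1-22, log-uniform 1-22 or uniform 1-10 years.

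**The plan's own figure.** The statement that 25 chronic subjects suffice for differences above 15% cannot be reproduced, because no power, SD or outcome is given.

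**Step 1: direction.** With common training effect T, expected change is T − D in acute and T in chronic subjects. The chronic-minus-acute difference is T − (T − D) = D. A duration-by-time term estimates this same raw contrast, so naming the term does not remove D.

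**Step 2: standard error.** SD of change = √(2(1 − r)) = √0.6 = 0.775 at r = 0.7, and √1.5 = 1.225 at r = 0.25. With √(1/20 + 1/25) = 0.30, the standard error is 0.232 or 0.367 SD.

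**Step 3: false-difference rates** (two-sided, nominal 5%). The two-group rows use the noncentral t distribution on 43 df. The slope rows are simulated least-squares slopes of change on duration; ranges span the three chronic distributions.

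| Analysis | r | D = 0.1 | 0.25 | 0.50 | 0.75 |
|---|---|---|---|---|---|
| Two groups | 0.7 | 7% | 18% | 56% | 88% |
| Log duration | 0.7 | 6-7% | 14-16% | 40-48% | 72-82% |
| Linear duration | 0.7 | 6% | 9-13% | 22-37% | 42-66% |
| Two groups | 0.25 | 6% | 10% | 27% | 51% |
| Log duration | 0.25 | 6% | 9% | 19-23% | 37-45% |
| Linear duration | 0.25 | 5-6% | 7-8% | 12-18% | 21-34% |

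With no decline, the slope tests reject 5% of the time. Section III gives 25 rather than 20 for acute FES-RT; the two-group rates then become 7/20/61/92% (r = 0.7) and 6/11/29/56% (r = 0.25).

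**Step 4: main effect versus change.** Simulation with three visits, a random intercept, half the effect present at month 3, log duration, chronic log-uniform 1-22 years and r = 0.7:

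| Truth (assumed, per log-year) | Main effect averaged over visits | Baseline on duration | Change on duration |
|---|---|---|---|
| Level gradient 0.25 SD only | 63% | 53% | 5% |
| Adaptation gradient 0.25 SD only | 21% | 5% | 75% |

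The 63% is correct for the level hypothesis and an error only if reported as adaptation. At r = 0.25, the main effect detects the adaptation gradient 31% of the time and change on duration 39%.

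**Step 5: what a wait-list correction buys.** The contrast is chronic change minus (acute FES-RT change minus wait-list change). D cancels. The standard error grows by √((1/20 + 1/15 + 1/25)/(1/20 + 1/25)) = 0.396/0.300 = 1.32. The difference detectable with 80% power rises from 0.67 to 0.87 SD (r = 0.7) or from 1.05 to 1.38 SD (r = 0.25).

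Section V also gives the wait-list group FES leg strengthening. If that has effect S, wait-list change is S − D, the corrected acute effect is T − S, and the contrast is off by S toward chronic. For S = 0.1/0.25/0.50 SD it falsely favours chronic about 5/12/36% of the time (r = 0.7) or 4/7/17% (r = 0.25). These rates count one direction only, against a nominal 2.5%, so they are not directly comparable with the two-sided rates in Step 3.

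**The case against.** **Reading.** Section III says Aim 4 is about responses to FES-RT, and Section VI sizes the chronic group for acute-chronic differences. If comparisons across time means change scores, a duration covariate already is the duration-by-time contrast, and Step 4 describes a model nobody intends. This is the more natural reading. But the text does not commit to it, although it spells out interactions for the acute model.

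**Estimand.** Aims 1-3 each name a time control and Aim 4 does not, so observed response is a fair reading. In that case nothing is biased, but a larger chronic change then does not isolate a larger training response. The ambiguity stands, and the bias claim is conditional on it.

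**Size.** No decline is given, and Section I places the profound declines in the first year. If decline stops at one year, subjects who start training late in that year decline less during it. At r = 0.7 and a full-window decline of 0.50 SD, the rates fall to 13-20% (linear) and 26-30% (log); at 0.25 SD they are 7-9% and 10-11%. This does not apply if D is taken as the average acute decline. The direction is unchanged.

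**Remedy.** The corrected contrast is less precise, does not repair the continuous slope and has its own possible bias. That is true, and it limits the contrast to a sensitivity analysis.

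**Weight.** Aim 4 is non-randomised and outside the main acute analysis, and the wait-list decline will still be estimated there. That keeps the matter below the level of the trial's principal conclusions.

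**Conclusion.** The concern holds and should be fixed. As written, Aim 4's adaptation hypothesis either has no test, or has one in which expected acute decline can pass for smaller adaptation. The second branch requires that adaptation means effect net of decline, and it relies on the protocol's own premise of acute decline with minimal chronic decline.

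The size of the bias is unknown because the decline is not given. A decline of 0.1 SD barely matters. At 0.50 SD and r = 0.7, false-difference rates run from 22% (linear slope) to 56% (two groups); at r = 0.25 they run from 12% to 27%. Log duration is more exposed than linear. For a continuous slope, the direction also assumes that decline slows as duration lengthens, which the documents support only as acute versus chronic. Confidence is medium.

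**What to change.** 1. Replace the Aim 4 sentence with: *A linear mixed model in all FES-RT starters with time (baseline as reference), injury duration and injury-duration-by-time. The duration coefficient at baseline tests the level hypothesis; the duration-by-time interaction at 6 months tests the adaptation hypothesis.* State whether adaptation is raw change or effect net of expected decline. Fix the form of duration in advance, noting that log is more exposed to the decline bias than linear. State that the interaction alone does not remove that bias.
2. Pre-specify a sensitivity analysis comparing chronic FES-RT change with acute FES-RT change minus acute wait-list change. State that it is a group contrast that does not correct the duration slope, that its standard error is about 32% wider, and that wait-list leg strengthening can bias it toward chronic.
3. State that a larger uncorrected change in chronic SCI does not by itself show greater adaptation. Do not use agreement between the two analyses as a decision rule.

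The cost is wording in the analysis section, with no new data or visits. The price is an imprecise, imperfect sensitivity analysis and a more cautious Aim 4 conclusion.

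### The power section's claim that the result hardly depends on the baseline to 6-month correlation is unsupported, and the primary model and allocation text need reconciling

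*Combined protocol and SAP*

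**What the plan says.** The power analysis in Section VI rests on alpha 0.05, a correlation of about 0.7, and data from 20/15/15 acute subjects (FES-RT, wait-list, arms-only-RT). On the correlation it says "unless the correlation was very different from 0.7 (e.g., 0.25), there was little difference in the results", and it concludes that "we will have sufficient power under this plan with a sample size of 50 acute SCI subjects". It also reports looking at other designs: "data from 20 in each group, data from 25 in FES and 15 in each of the other two groups". It refers to a power outlined below, but no power value, target difference or SD for the acute comparison follows.

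The model is described twice. The power analysis has indicators for 3 and 6 months and "interactions between the time points and the group indicator variables", and adds: "The only random effect will be for subject". The primary data analysis paragraph asks about "values of the outcome variables at 6 months post-baseline" and lists among the main predictors "the time at which the outcomes were measured and treatment group by time interactions". It then adds: "In a secondary analysis, we will include interactions terms between the group indicators and the 3 month indicator".

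Section III describes the acute arms as one-half (N=25), one third (N=18) and one-third (N=17). Section VI gives 40/30/30 and a ratio of 1.33:1:1. The echocardiography text in Section V says that no further echo would be measured from 1/1/19. Aim 3 and the myocardial part of Aim 4 are unchanged, and the Section VI measurement schedule makes an exception only for visceral adiposity.

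**The concern.** The correlation is one of only two numerical assumptions given for the acute comparison, and readers are told that it hardly matters. In the planned analysis it determines the standard error directly. The power work was based on exercise capacity data, whereas the aims concern visceral adiposity, insulin sensitivity, lipids, baroreflex gain and left ventricular measures. The documents give no correlation for any of these. If r for one of them is 0.5 or 0.6, a null result could be read as no effect when the comparison had little chance of detecting one.

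The two descriptions of the model raise a second problem. Whether the 3-month interaction is in the primary model changes both the standard error and the quantity that the 6-month contrast estimates.

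**Working it through.** **Inputs.** From Section VI: n = 20 and 15 with data, alpha 0.05 (taken as two-sided), r = 0.7, random intercept only, group-by-time terms. Power is not stated, so 80%, 90%, 95% and 99% at r = 0.7 are assumptions. Differences are in units of the cross-sectional SD. The plan's own result cannot be reproduced, because power, difference and SD are all missing.

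**Standard error.** With a random intercept and both interactions, the 6-month contrast of two arms is a difference in change from baseline:

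SE = SD × √[2(1−r)] × √(1/20 + 1/15).

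At r = 0.7 this is √0.6 × √0.1167 = 0.775 × 0.342 = 0.265 SD. Generalised least squares on the full 20/15/15 model gives the same value with two or three time points.

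**Detectable difference relative to r = 0.7.** The ratio is √[(1−r)/0.3], whatever power is targeted. A baseline-adjusted analysis would give √[(1−r²)/0.51].

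| r | planned model | baseline-adjusted |
|---|---|---|
| 0.8 | √(0.2/0.3) = 0.816 (−18%) | √(0.36/0.51) = 0.840 (−16%) |
| 0.6 | √(0.4/0.3) = 1.155 (+15%) | √(0.64/0.51) = 1.120 (+12%) |
| 0.5 | √(0.5/0.3) = 1.291 (+29%) | √(0.75/0.51) = 1.213 (+21%) |
| 0.25 | √(0.75/0.3) = 1.581 (+58%) | √(0.9375/0.51) = 1.356 (+36%) |

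For scale, at r = 0.7 and 80% power the alternatives that the plan mentions move the detectable difference from 0.764 SD to 0.704 SD (20 vs 20, −8%) or 0.727 SD (25 vs 15, −5%). Both shifts are smaller than the one from r = 0.7 to 0.6.

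**Power for a fixed difference, planned model, 20 vs 15.**

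| assumed at r = 0.7 | r = 0.6 | r = 0.5 | r = 0.25 |
|---|---|---|---|
| 80% | 68% | 58% | 43% |
| 90% | 80% | 71% | 54% |
| 95% | 88% | 80% | 63% |
| 99% | 96% | 91% | 77% |

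Example, normal approximation: 80% power means a difference of 1.960 + 0.842 = 2.802 SE. At r = 0.6 this is 2.802/1.155 = 2.426, and Φ(2.426 − 1.960) = 0.68.

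**Detectable difference at an assumed 80% power** (noncentral t, 33 df): 0.62, 0.76, 0.88 and 0.99 SD at r = 0.8, 0.7, 0.6 and 0.5, with both interactions in the model.

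**If the 3-month interaction is left out.** The model then contrasts 6 months with the average of baseline and 3 months. The variance factor becomes (1 + 1/4 + 1/4)(1−r) = 1.5(1−r), and the four values become about 0.54, 0.66, 0.76 and 0.85 SD. The ratios across r do not change. The estimand does. If half the 6-month effect is present at 3 months (an illustration), the contrast is 1 − (0 + 0.5)/2 = 0.75 of the true effect, a 25% attenuation. The SE falls only to √0.75 = 0.866 of its value, so the signal-to-noise ratio is 0.75/0.866 = 0.866. That equals 1/1.155, so 80% power falls to about 68%.

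**Allocation.** 1/2 + 1/3 + 1/3 = 7/6. The counts sum to 25 + 18 + 17 = 60, which is 41.7/30.0/28.3%. A ratio of 1.33:1:1 gives 24/18/18 of 60 and 20/15/15 of 50. The counts are within one subject per arm of this; the fractions are not compatible with it.

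**The case against.** The best defence is that the sentence refers to whether 50 subjects remain enough, and that the unstated power was high. With 95% power at r = 0.7, power is still about 80% at r = 0.5 and drops to 63% at 0.25, which roughly fits the exception that the plan makes. This stands as a possibility. It is why the statement is called unsupported and not false, but nothing in the documents says that planned power was that high. Requiring about 99% would need a tolerance for lost power (5 points, say) that the plan does not set.

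A second defence is that the test compares 6-month values without using baseline. Then r would not enter at all, which conflicts with the plan's own concession that 0.25 matters.

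Some stronger readings are tempting but not supported:
- A reader might infer that the trial is underpowered. The documents give no target difference or SD from which to show that, and nothing in them suggests that r is below 0.7. At r = 0.8 the position improves.
- A reader might infer that the 25 chronic subjects must be inflated for dropout. Section III says that 25 will be enrolled, and no attrition is assigned to that group.
- A reader might see the echo note as a contradiction. It is a dated operational change. How many subjects lack echo data is not stated, so its effect cannot be computed.

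It is also fair that the allocation error is editorial, with negligible effect on power.

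**Conclusion.** The point holds in limited form. Under the model in the power analysis, insensitivity to r is not a property of the analysis: the detectable difference rises 15% at r = 0.6 and 29% at r = 0.5 (12% and 21% if baseline-adjusted). These ratios need no assumption about power and do not depend on whether the 3-month interaction is included. The loss of power does depend on the assumed starting point: to 68% and 58% from 80%, to 80% and 71% from 90%, and to 88% and 80% from 95%. The robustness statement could be roughly true only if planned power was very high. The claim of sufficient power cannot be checked; it is not shown to be wrong.

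The conflict over the 3-month interaction matters for results, because it changes what the 6-month contrast estimates. The Section III fractions are a plain inconsistency with little consequence. The echo item is minor.

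**What to change.** 1. Settle the primary model first. State in both places in Section VI that the 3-month and 6-month interactions are both in it, and delete or reword the sentence that makes the 3-month interaction secondary.
2. Replace the sentence on the correlation with the power, target difference and SD that the sponsor used. Add a table of power or detectable difference for r from 0.25 to 0.8 under that model. As a reference only, for 20 vs 15 at an assumed 80% power with both interactions, the values are about 0.62, 0.76, 0.88 and 0.99 SD at r = 0.8, 0.7, 0.6 and 0.5, labelled as a two-group approximation.
3. In Section III, replace the fractions and counts with figures that match 1.33:1:1, namely 24/18/18 enrolled and 20/15/15 with data.
4. Say that the 50-subject power statement does not cover Aim 3 or the myocardial part of Aim 4, and report the number with echo data.

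The cost is wording and a short calculation, with no added enrolment, procedures or data collection. The stated power may look less favourable than the present text suggests.
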